# 7.0 STATISTICAL CONSIDERATIONS

#### 7.1 Sample Size and Accrual

We will enroll 25 adult subjects with suspected with suspected kidney cancer and planned surgical nephrectomy. We have deep recruitment experience for kidney CEUS imaging. Approximately 150 nephrectomies for localized disease are performed at UNC yearly. Based on our previous recruitment rate of ~75% and a strong partnership with our urology colleagues, we anticipate no problems meeting our recruitment goal of 25 subjects.

#### 7.1.1 Primary Objective

# 7.1.1.1 Predicting kidney mass diagnosis using 3D CEUS generated metrics.

The proposed sample of 25, assuming 60% clear cell legions, achieves 63.2% power to detect a difference of 0.1000 between a diagnostic test with an area under the ROC curve (AUC) of 0.8000 and another diagnostic test with an AUC of 0.9000 using a two-sided z-test at a significance level of 0.050. The correlation between the two diagnostic tests is assumed to be 0.9 for the positive group and 0.9 for the negative group.

The proposed sample of 25, assuming 60% clear cell legions, achieves 88.7% power to detect a difference of 0.1500 between a diagnostic test with an area under the ROC curve (AUC) of 0.8000 and another diagnostic test with an AUC of 0.9500 using a two-sided z-test at a significance level of 0.050. The correlation between the two diagnostic tests is assumed to be 0.9 for the positive group and 0.9 for the negative group.

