#### 7.1.2 Secondary Objectives

# 7.1.2.1 To compare diagnostic accuracy of F-R infusion imaging technique to low MI bolus imaging technique.

The proposed tests with sample size 25 have 63.2% power to detect a difference of 0.1 in the AUCs (.8 vs .9) and 88.7% power to detect a difference of 0.15 (0.8 vs 0.95).

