standard of histologic diagnosis to differentiate clear cell from non-clear cell tumors, we will use logistic regression to build predictive models based on multiple parameters from CEUS (WI, WO, MTT, TTP, PE and tumor volume), B-mode US images (length, echogenicity, shape), as well as patient factors (age, sex, race) (Table 1). We will assess the effects of individual parameters using hypothesis tests based on parameter estimates from the fitted logistic regression model. This approach facilitates assessment of the added value of the CEUS measurements over other patient factors. We will calculate nonparametric estimates and 95% confidence intervals for area under the curve (AUC) using the fitted logistic regression models, both with and without non-CEUS patient factors. We will use model selection procedures, including AUC, to identify a final model, with a one-sided test of AUC  $\leq .8$  vs AUC  $\geq .8$  at alpha=.05 for the final model. We will use model selection procedures based on optimizing AUC to identify a final model, with a one-sided test of AUC<=0.8 vs AUC>=.8 at alpha=.05 for the final model.

Gold Standard Comparator: Histologic diagnosis from pathologic tissue.

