# 7.2.2 Comparing diagnostic accuracy of F-R infusion imaging technique to low MI bolus imaging technique.

Image Analysis (Flash-Replenishment TIC analysis): For each 0.5-1 cm step, we will produce a TIC by delineating an ROI of the entire mass and measuring the mean contrast signal intensity over the time course of the F-R. We will model TIC using a mono-exponential equation, UI=A(1 -  $e^{-\beta t}$ ), where UI is ultrasound intensity and  $\beta$ , the slope of the tangent to the curve, represents the rate of perfusion. The height of the curve, A, represents the perfusion volume. To produce a single value for  $\beta$  for the entire tumor volume, we will calculate a weighted average based on the ROI area of the mass at each step. This value will serve as the WI rate.

Gold Standard Comparator: Histologic diagnosis from pathologic tissue.

*Statistical Analysis:* We will follow the model building and evaluation strategy used for the primary objective. This will be done separately for bolus and infusion imaging modalities, as well as combining the two multiparametric scores. We will compare AUCs from final logistic regression models obtained for bolus and infusion using a Z-test at alpha=0.05, with standard errors obtained by bootstrapping correctly adjusting for the fact that the two AUCs are calculated using the same data and hence correlated. We will conduct similar tests comparing the AUC based on the combined model to those based on bolus and infusion multiparametric scores separately. The proposed tests with sample size 25 have 80% power to detect a difference of .1 in the AUCs (0.8 vs 0.9) and 90% power to detect a difference of 0.15 (0.8 vs 0.95).

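### The power given for the primary objective (63.2% and 88.7%) is for a two-sided comparison of two correlated AUCs; the primary test is one-sided, of one AUC against 0.8, and its power is not stated

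*Combined protocol and SAP*

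**What the plan says.** Under the primary objective, section 7.1.1.1 assumes 60% clear cell lesions among 25 subjects. It states that the sample "achieves 63.2% power to detect a difference of 0.1000 between a diagnostic test with an area under the ROC curve (AUC) of 0.8000". The comparator and the test are then given as "another diagnostic test with an AUC of 0.9000 using a two-sided z-test at a significance level of 0.050". A second paragraph gives 88.7% for AUCs of 0.80 and 0.95. Both paragraphs add: "The correlation between the two diagnostic tests is assumed to be 0.9 for the positive group and 0.9 for the negative group".

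Section 7.2.1 sets out the primary analysis. Logistic models separate clear cell from non-clear cell masses, using CEUS, B-mode and patient factors. On the choice of model it says: "We will use model selection procedures based on optimizing AUC to identify a final model". The hypothesis test attached to that choice reads: "with a one-sided test of AUC<=0.8 vs AUC>=.8 at alpha=.05 for the final model". AUC estimates with confidence intervals are planned "both with and without non-CEUS patient factors", but no test of that difference is specified. The other hypothesis tests in 7.2.1 concern individual regression parameters, not AUCs.

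Section 7.1.2.1 repeats the figures for bolus versus infusion: "The proposed tests with sample size 25 have 63.2% power to detect a difference of 0.1 in the AUCs", with 88.7% for a difference of 0.15. That comparison does involve two AUCs. In section 7.2.2: "We will compare AUCs from final logistic regression models obtained for bolus and infusion using a Z-test at alpha=0.05". The same paragraph of 7.2.2 puts its power at 80% and 90% for the same two differences.

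**The concern.** The powered test and the planned primary test differ in three ways: two AUCs against one AUC and a constant, two-sided against one-sided, and a correlation of 0.9 against none. One-sidedness raises power. Replacing a comparator correlated at 0.9 with a fixed value removes the cancellation of shared sampling error, which lowers it.

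Section 7.1.1.1 is the only statistical support for 25 subjects on the primary objective; section 7.1 otherwise argues from recruitment. A reader would take 63.2% and 88.7% as the chance that the primary test succeeds at true AUCs of 0.90 and 0.95. A non-significant result would then be read as stronger evidence against the technique than it is.

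**Working it through.** **Inputs from the documents.** N = 25 and 60% clear cell, so m = 15 and n = 10. AUC 0.80 against 0.90 or 0.95. Two-sided alpha 0.05 and correlation 0.9 (7.1.1.1). One-sided alpha 0.05 against the fixed value 0.8 (7.2.1).

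**Assumptions added here.** A score fixed in advance, with binormal distribution in the simulations. The plan names no standard error (SE) for the primary test, so several are shown.

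**Step 1: standard errors (Hanley-McNeil).** SE² = [A(1−A) + (m−1)(Q1−A²) + (n−1)(Q2−A²)]/(mn), with Q1 = A/(2−A) and Q2 = 2A²/(1+A).
- At A = 0.80: (0.16 + 14×0.0267 + 9×0.0711)/150 = 0.00782, so SE0 = 0.0884.
- At 0.90, SE = 0.0626. At 0.95, SE = 0.0438.

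**Step 2: reproduce the plan's figures as paired power.** Power = Φ((d − 1.96√V0)/√VA), with V0 = 2·SE0²(1−r) and VA = SE0² + SE1² − 2r·SE0·SE1.
- With r = 0.88 between the AUC estimates, √V0 = 0.0433.
- d = 0.10: (0.10 − 0.0849)/0.0447 = 0.34, power 63.2%.
- d = 0.15: (0.15 − 0.0849)/0.0541 = 1.20, power 88.6%.

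The 0.88 was chosen because it fits; it reads the plan's 0.9 as a correlation of ratings. Using 0.9 directly between AUCs gives 70.3% and 91.6%. A binormal (Obuchowski-McClish) formula at rating correlation 0.9, with nothing fitted, gives 65.2% and 87.5%. One-sided versions do not fit (74-75% and 91.5-92.7%). The stated figures are therefore two-sided paired power by formula.

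**Step 3: the test in 7.2.1, by formula.** Power = Φ((d − 1.645·SE0)/SE1), with 1.645×0.0884 = 0.1455.
- AUC 0.90: (0.10 − 0.1455)/0.0626 = −0.73, power about 23%.
- AUC 0.95: (0.15 − 0.1455)/0.0438 = 0.10, power about 54%.

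**Step 4: the same test by simulation** (100,000 datasets per AUC).

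| One-sided test against 0.8 | Type I error | Power at 0.90 | Power at 0.95 |
|---|---|---|---|
| Null SE 0.0884 | 4.0% | 27.8% | 63.6% |
| Logit DeLong, sample AUC of 1 rejects | 4.6% | 30.0% | 64.8% |
| Logit DeLong, sample AUC of 1 does not reject | 4.4% | 27.5% | 53.5% |
| Calibrated cut-off, sample AUC at least 0.94 | 4.9% | 32.1% | 68.5% |
| Wald DeLong, uncorrected | 12.0% | 52.5% | 85.3% |

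The rule for a sample AUC of 1 matters because it occurs in 2.5% of datasets at 0.90 and 11.3% at 0.95.

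**Step 5: the paired test by simulation.** The two-sided paired DeLong test with 15 and 10 subjects reaches about 34% and 58% at rating correlation 0.9, with about 2% type I error. At correlation 0.8 it reaches about 23% and 49%.

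**Step 6: compare like with like.**

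| Basis | Paired (0.90; 0.95) | One-sample (0.90; 0.95) |
|---|---|---|
| Formula | 63-65%; 88-89% | 23%; 54% |
| Simulation, type I error at or below 5% | 34%; 58% | 27-32%; 53-68% |

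By formula the mismatch costs about 40 points at 0.90 (63.2 − 23) and 35 at 0.95 (88.7 − 54). By simulation the two tests have similar power.

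**The case against.** **The paired figures may refer to models with and without other factors.** Section 7.2.1 does plan both AUCs on the same subjects, where a high correlation is plausible. But it attaches no test to the difference. If that contrast was meant to be primary, the omission lies in 7.2.1 instead, and the two sections still disagree. The fix allows for this.

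**A Wald DeLong test comes close to the stated figures.** It gives about 52% and 85%, within about 11 and 4 points, and the plan does not exclude it. It does so by rejecting a true null about 12% of the time at a nominal 5%. This is a reason to name the SE method.

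**The shortfall mixes methods.** This stands. A reader might infer that the mismatch alone costs 31 to 36 points at AUC 0.90 and 20 to 35 at 0.95. Those gaps set simulated one-sample power against formula paired power, and step 6 shows that the mismatch's share depends on the basis.

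**Model selection changes the rejection rate.** This also stands. In an illustrative check (12 independent candidates, one informative, forward selection of two or three terms by apparent AUC, no optimism correction), the logit test rejected in 64-77% of runs when the informative factor had AUC 0.90. It also rejected in 21-37% when that AUC was only 0.80, so much of the rate is optimism. A reader might infer that the written procedure has less chance of success than 63.2%; the documents do not support that, because the rate under selection is not determined.

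**This is a small study, and N rests partly on accrual.** That limits the consequence, but the plan still states a power for the primary objective that belongs to another test.

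**Conclusion.** The point holds. The 63.2% and 88.7% in section 7.1.1.1 are formula values for a two-sided test of two correlated AUCs. They do not describe the one-sided test of one AUC against 0.8 in section 7.2.1, whose power is stated nowhere.

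For a pre-specified score, a 15/10 split and type I error near or below 5%, that test has about 23-32% power at AUC 0.90 and 53-68% at 0.95, taking formula and simulation together. The direction is firm across these methods; the exact size depends on the SE and on how a sample AUC of 1 is treated.

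Two stronger readings go too far. The gap from the stated figures is not all due to the mismatch. Nor can the paired figures simply be treated as sound for the bolus-versus-infusion test in 7.1.2.1: the formula supports them, but simulation at N = 25 does not.

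**What to change.** 1. In 7.1.1.1, replace the paired figures with power for the one-sided, one-sample test against 0.8. Name the SE method and the rule for a sample AUC of 1. For example, logit-scale DeLong by simulation gives about 30% at 0.90 and 65% at 0.95 if a sample AUC of 1 counts as rejection, and about 27% and 53% if it does not. State that these assume a pre-specified score and do not cover selection of the model by AUC on the same subjects.
2. If the paired paragraphs are kept for bolus versus infusion in 7.1.2.1, carry over their assumptions (60% clear cell, two-sided, correlation 0.9) and label them as large-sample formula values. Give the simulated values beside them: about 34% and 58% at correlation 0.9, about 23% and 49% at 0.8. Reconcile them with the 80% and 90% in 7.2.2.
3. Alternatively, if a paired contrast was intended as primary (such as models with and without the CEUS metrics), name the comparator and the two-sided paired test in 7.2.1. State its power on the same simulated basis and justify the correlation.

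The cost is protocol wording and a short simulation. Sample size and conduct do not change. The stated power becomes less favourable, and the SE method and the rule for a sample AUC of 1 must be fixed before analysis.

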#### 1.6 Contrast Enhanced Ultrasound

CEUS has several features that distinguish it from contrast CT/MRI. Unlike contrast CT/MRI, CEUS captures real-time images, enabling dynamic visualization of contrast over time. In addition, the CEUS contrast agent, microbubbles, remains intravascular, and is thus sensitive to lesion enhancement and small vessel involvement, giving CEUS the potential to inform kidney mass staging and surgical planning, capabilities not currently possessed by CT/MRI.

In addition, CEUS microbubbles differ from CT/MRI contrast agents in that they are cleared by the lungs within minutes of administration and have no known nephrotoxicity, making CEUS safe for patients with advanced CKD. For these individuals, CEUS availability would mean access to contrastenhanced imaging, which would significantly improve the ability to provide a definitive mass diagnosis and increase the chance of avoiding unnecessary surgery. CEUS maintains the advantages of conventional US (lower cost in comparison to CT/MRI and safety).

To-date, most CEUS research has utilized a 2D approach. By adapting routine imaging techniques, we can generate three-dimensional (3D) CEUS images. Our preliminary work suggests that expanding 2D CEUS to a 3D technique will provide deeper data about mass enhancement, facilitating subtype differentiation. Moreover, our group has developed image analysis techniques that can generate 3D renderings of the vasculature (described below).

In 2D or 3D CEUS, microbubbles can be administered by bolus or continuous infusion dosing which correspond with low mechanical index (MI) and flash-replenishment imaging (F-R), respectively. The two approaches yield different information. The optimal approach is unknown.

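### The 63.2% and 88.7% power stated for infusion versus bolus rests on an unsupported, optimistic within-class correlation of 0.9 that Section 7.1.2.1 does not restate

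*Combined protocol and SAP*

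**What the plan says.** Section 7.1 sets the sample: "We will enroll 25 adult subjects". Section 7.1.1.1 then gives the power: "The proposed sample of 25, assuming 60% clear cell legions, achieves 63.2% power". That figure belongs to the first scenario, "area under the ROC curve (AUC) of 0.8000 and another diagnostic test with an AUC of 0.9000". The second scenario, with 88.7% power, is "area under the ROC curve (AUC) of 0.8000 and another diagnostic test with an AUC of 0.9500". In both, the comparison is made "using a two-sided z-test at a significance level of 0.050". The remaining input is stated for both: "The correlation between the two diagnostic tests is assumed to be 0.9 for the positive group and 0.9 for the negative group". Section 7.1.1.1 does not say which two tests are meant.

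Section 7.1.2.1 reuses the results for the secondary objective of comparing the two imaging techniques: "The proposed tests with sample size 25 have 63.2% power to detect a difference of 0.1 in the AUCs (.8 vs .9"). For 0.8 vs 0.95 it gives 88.7%. It does not mention the correlation. Section 7.2.2 describes the test as a Z-test at 0.05 on the AUCs of the final bolus and infusion models, with bootstrap standard errors that allow for the pairing. It then claims 80% and 90% power for the same two differences and the same 25 patients.

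On the techniques themselves, Section 1.6 says: "The two approaches yield different information". It adds that the infusion curve provides no wash-out rate and that the accuracy of infusion dosing is unknown. Section 7.2.2 also plans to test whether the combined scores do better than either score alone.

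**The concern.** When two AUCs come from the same patients, the variance of their difference depends heavily on how closely the two scores track each other within the clear cell group and within the non-clear cell group. A correlation of 0.9 makes the two scores near-duplicates, which shrinks that variance and raises the power. The plan offers no pilot estimate, citation or argument for 0.9. Its own description of the techniques, and its interest in combining the scores, do not fit comfortably with near-duplicates. Someone reading 7.1.2.1 alone cannot see that the power depends on this input.

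Objective 2.2.1 is a head-to-head comparison that the protocol says is unresolved. With power of 88.7% on paper for a difference of 0.15, a non-significant result would look like fair evidence that the techniques perform alike. If the real power is far lower, the same result says little.

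**Working it through.** **Inputs.** From Section 7.1.1.1: 25 patients, 60% clear cell, so n1 = 0.60 × 25 = 15 and n0 = 10; AUC 0.80 vs 0.90 and 0.80 vs 0.95; two-sided 0.05; correlation r = 0.9 in both groups. Two things are my assumption: equal score variances in the two groups, and any r other than 0.9, since the documents give no other value.

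**Formula.** Large-sample binormal (Obuchowski–McClish) variance for two correlated AUCs. For AUC θ:
- a = √2·Φ⁻¹(θ), f = exp(−a²/4)/√(4π), g = −a·exp(−a²/4)/√(16π)
- V(θ) = f²[1/n1 + 1/n0 + a²/(2n1)] + g²(n1+n0)/(2n1n0) + f·g·a/n1
- C(θ1,θ2) = f1f2[r/n1 + r/n0 + r²a1a2/(2n1)] + g1g2·r²(n1+n0)/(2n1n0) + r²(f1g2a1 + g1f2a2)/(2n1)
- SE0² = 2V(0.8) − 2C(0.8,0.8); SE1² = V(0.8) + V(θ2) − 2C(0.8,θ2)
- Power = Φ[(θ2 − 0.8 − 1.96·SE0)/SE1]

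**Reproducing the plan's figures (r = 0.9).** V(0.8) = 0.007688, V(0.9) = 0.003620, V(0.95) = 0.001486; C(0.8,0.8) = 0.006815, C(0.8,0.9) = 0.004579, C(0.8,0.95) = 0.002840.
- SE0 = √(0.015376 − 0.013630) = 0.0418
- 0.8 vs 0.9: SE1 = √(0.011308 − 0.009158) = 0.0464; (0.10 − 0.0819)/0.0464 = 0.39; power 65.2% (stated 63.2%)
- 0.8 vs 0.95: SE1 = √(0.009174 − 0.005680) = 0.0591; (0.15 − 0.0819)/0.0591 = 1.15; power 87.5% (stated 88.7%)

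Both are within 2 points of the stated figures, so the plan's arithmetic is in order for the inputs that it chose.

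**Changing only the correlation.** The simulation column is a paired DeLong z-test on binormal scores, 15 vs 10, about 20,000 runs per cell. It stands in for the planned bootstrap z-test and takes the scores as given, with no model building. Repeat runs differed by about a point.

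| r | SE0 | SE1 (0.9 / 0.95) | Formula power (0.9 / 0.95) | Simulated power (0.9 / 0.95) |
|---|---|---|---|---|
| 0.9 | 0.0418 | 0.0464 / 0.0591 | 65% / 88% | 33% / 58% |
| 0.8 | 0.0587 | 0.0578 / 0.0653 | 40% / 70% | 23% / 49% |
| 0.7 | 0.0714 | 0.0670 / 0.0706 | 28% / 56% | 19% / 42% |
| 0.5 | 0.0909 | 0.0816 / 0.0797 | 17% / 36% | 15% / 34% |

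**Does the choice of formula matter?** At r = 0.9, using the alternative standard error only gives 57.8%/71.8%, Hanley–McNeil 66.1%/81.3%, and a simplified Obuchowski variance 62.7%/87.0%. Over r = 0.5 to 0.7, all the formulas tried span 15–35% and 31–63%. The exact percentage depends on the formula; the steep fall does not.

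**Where the shortfall comes from.** For 0.8 vs 0.9, going from the stated 63.2% to the simulated 33% at r = 0.9 costs 63.2 − 33 ≈ 30 points, before the correlation changes. Lowering r to 0.7 costs a further 33 − 19 = 14. For 0.8 vs 0.95 the steps are 88.7 − 58 ≈ 31 and 58 − 42 = 16. The large-sample approximation at this sample size therefore contributes more than the correlation does.

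**The case against.** The strongest reply is that 0.9 could be right. Both techniques image the same mass, in sequence. The models may share B-mode length, echogenicity and shape, tumor volume, and age, sex and race, and both techniques yield a wash-in rate. Shared predictors push the two model scores together. The remark in Section 1.6 describes the raw curves, not the correlation of the final scores, and a plan to combine scores does not show that they are weakly correlated. All of this stands. A reader might infer that the protocol argues against its own 0.9; it does not. It simply never argues for it.

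A reader might also take 0.9 as the best case. It is not: the same formula gives 85.7%/95.1% at 0.95. Optimistic is the accurate word. Nor do the documents support 0.5 to 0.7 as the true range.

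It is fair to add that the assumption is disclosed in 7.1.1.1, that the figures reproduce, that 63.2% is already modest for a secondary objective, and that nowhere does the plan propose to claim equivalence. These points limit the severity. They do not answer the fact that 7.1.2.1 gives single figures without the input that drives them, or that the simulated paired test falls well short of those figures even when 0.9 is granted.

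**Conclusion.** The point holds as a fault in a planning assumption and its reporting, not in the arithmetic. A drop in correlation from 0.9 to 0.8 alone takes the formula power from about 65% to 40% for a difference of 0.1, and from about 88% to 70% for 0.15. A simulated paired z-test at 15 vs 10 gives about 33% and 58% at 0.9, so the design is unlikely to have the stated power at any correlation from 0.5 to 0.9.

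This rests on binormal scores with equal variances, a 15/10 split, and DeLong standard errors in place of the bootstrap. The link between the unnamed tests in 7.1.1.1 and the two techniques is inferred from the identical figures in 7.1.2.1.

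A reader might infer that the primary analysis is affected too. The documents do not support that: Section 7.2.1 tests one final-model AUC against 0.8, and a correlation between two tests plays no part in it. The point concerns objective 2.2.1 only. It should be corrected, but it does not threaten the conduct of the study.

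**What to change.** - In 7.1.2.1, and in the power sentence of 7.2.2 that now says 80% and 90%, replace the single figures with one table of power over a range of within-class correlations, for example 0.5 to 0.9. Preferably obtain it by simulating the planned paired z-test with 15 and 10 patients. Both sections should then give the same numbers.
- State the correlation beside the power. Either justify 0.9 (for instance from pilot scores or the shared predictors) or describe it as an optimistic assumption. Do not call it the best case.
- Add that a non-significant difference will not be read as equal accuracy, and that the AUC difference will be reported with its confidence interval. Section 7.1.2.2 already takes a similarly candid line for staging.

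The cost is wording and a short simulation. No additional patients, visits or imaging are needed. The downside is a less favourable stated power for objective 2.2.1.
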